### Protocol Amendments:

Amendment No.	Date of Amendment	Date of Approval

## STUDY SUMMARY

Trial Title	Assessment of safety of a medieval antibiotic to treat infected diabetic ulcers: a Phase 1 trial in healthy volunteers
Sponsor ref. number	
Clinical Phase	Phase I
Trial Design	Single centre non-randomised, uncontrolled intervention study
Trial Participants	Healthy volunteers, aged from 18 to 79 years
Planned sample size	100 participants
Treatment Duration	48 hours
Follow-up Duration	48 hours
Planned Trial Period	1 April 2021 to 1 July 2021 (3 months)
Objectives	
To aim is to determine the safety of an ‘ancientbiotic’ (Bald’s salve) when applied to the skin of human volunteers. The ancientbiotic is a mixture of natural products used in a historical infection remedy.
 
The specific objective is to determine the frequency of adverse events associated with a patch test of Bald’s salve applied to the skin of human volunteers.

Outcomes	
Primary	Skin irritation assessed at 48 hours.
Secondary	Any other adverse event associated with the patch test application of Bald’s salve.

## LIST OF ABBREVIATIONS/GLOSSARY

---

Abbreviation	Explanation
AE	Adverse Event
CI	Chief Investigator
CONSORT	Consolidated Standards of Reporting Trials
CRF	Case Report Form
CTU	Clinical Trials Unit
DMC	Data Monitoring Committee
DFI	Diabetic Foot Ulcer
GCP	Good Clinical Practice
IRAS	Integrated Research Application System
ISRCTN	International Standard Randomised Controlled Trial Number
MRSA	Meticillin-resistant Staphylococcus aureus
PI	Principal investigator
PPI	Patient & Public Involvement
RCT	Randomised controlled trial
REC	Research Ethics Committee
R&D	Research and Development
SAE	Serious Adverse Event
SOP	Standard Operating Procedure
TSC	Trial Steering Committee
WCTU	Warwick Clinical Trials Unit

---

## 1. BACKGROUND

### 1.1 Burden of diabetic foot ulcers

People with diabetes risk developing ulcers on their lower limbs. Hyperglycaemia, poor circulation and abnormal immune responses mean that ulcers become infected by bacteria. Ten percent of people with Type 1 or Type 2 diabetes develop chronic, non-healing infected ulcers. Diabetic foot infections (DFIs) are a key cause of hospitalisation and severely impact quality of life. Even if a DFI is successfully treated, there is a high chance of recurrence, with up to 66% recurring. Consequences of DFI include amputation and sepsis; up to 12% of people with DFI require an amputation. Approximately half of people with DFIs die within five years of ulcer development. Management of DFIs costs the NHS £600M per year, and the burden of infection will likely increase as the prevalence of Type 2 diabetes rises.

Key pathogens in DFIs include common causes of other opportunistic infections, e.g. *Staphylococcus aureus*, *Pseudomonas aeruginosa*, *Escherichia coli*, *Streptococcus spp.*, *Enterococcus spp.* and *Klebsiella pneumoniae*. DFIs typically comprise a diverse community of different bacterial species which live as a multicellular biofilm: a community of bacteria protected by a slime layer that hinders immune clearance and antibiotic penetration. Furthermore, widespread antibiotic use has led to bacteria evolving various genetic strategies to become resistant to drugs currently in use. The problem of untreatable DFI will likely worsen due to a scarcity of new antibiotics in development. We desperately need new antibiotics to effectively treat DFIs. Antimicrobial resistance has been highlighted by the World Health Organization (WHO) as a global health emergency.

### 1.2 The hunt for new antibiotics by studying the past

The research team have used ethnopharmacology (the study of traditional and historical medicine) to find compounds that could be tested and developed into new antibiotics. Medieval European medical texts contain abundant remedies for infections, often using ingredients shown to have antimicrobial qualities *in vitro*. Some of these have already produced clinical antimicrobials e.g. honey dressings, or *Artemisia spp.*, which produce the anti-malarial drug artemisinin.

We found that a medieval English remedy for eye infections kills various bacteria found in DFIs and other persistent infections. This ‘ancientbiotic’ is made by combining garlic, onion, bovine bile and wine, and allowing the mixture to steep for nine days. The recipe was chosen for study as all ingredients are known to have some (limited) antibacterial activity *in vitro*. The remedy’s efficacy depends on preparing and combining ingredients as specified in the original text. While the well-studied compound allicin, from garlic, explains the ability of the remedy to kill bacteria growing in liquid broth culture, allicin alone cannot kill bacteria in biofilms at the concentrations it is found in the remedy. This could explain why *in vitro* antibacterial activity of the individual ingredients does not reliably translate into *in vivo* potential in clinical trials e.g. garlic. This result is crucial: something happens when the ingredients are combined, generating a cocktail of compounds and/or a novel compound which effectively kills bacteria.

## 1.3 Could an ancientbiotic generate a treatment for infections?

### 1.3.1 Bald's salve kills a range of clinically-relevant bacteria when grown as biofilms

Bacteria are relatively easy to kill when they are grown as free-swimming cells in liquid cultures in test tubes. Many natural products (compounds made by plants, animals or microbes) can kill pathogenic bacteria when grown in this state. But when bacteria form matrix-embedded, multicellular biofilms – as they do in diabetic ulcers – their tolerance to antibacterial compounds is massively increased. Bacteria that are susceptible to low concentration of antibiotics in a test tube may require a 1,000-fold higher antibiotic concentration for effective biofilm killing, and natural products with promising antibacterial activity in a test tube may fail to kill bacteria in biofilms.

Activity against biofilms is what makes Bald's salve stand out as a promising candidate for clinical development. We have made over 70 batches of the salve, and they are all able to kill mature biofilms of the bacterium *S. aureus* in an *in vitro* model of a diabetic wound biofilm. Mature biofilms comprise approximately  $10^8$  bacterial cells, but exposure to the salve for 24 hours results in only 100-1,000 bacteria surviving. This represents a 5-6  $\log_{10}$ -fold killing effect. In microbiology, a 3  $\log_{10}$ -fold killing effect in lab studies is generally taken to represent good bactericidal activity worthy of further investigation.

We have also shown that Bald's salve can kill biofilms of a methicillin-resistant strain of *S. aureus* (MRSA) when biopsies of biofilm-infected tissue from wounded mice are placed into a suspension of the salve, and that the salve kills these tissue-embedded biofilms more quickly than the current gold standard antibiotic for MRSA. Further, we have recently confirmed that Bald's salve can kill biofilms of other important diabetic foot ulcer bacteria: *Acinetobacter baumannii*, *Stenotrophomonas maltophilia*, *Staphylococcus epidermi, dis* and *Streptococcus pyogenes*. Activity against *A. baumannii* is especially noteworthy as this is a WHO priority pathogen with extensive intrinsic resistance to numerous antibiotics. While the presence of allicin from garlic in Bald's salve can explain the activity against free-swimming bacterial cells, the salve contains allicin in concentrations much lower than that required to kill biofilms: all ingredients are required to produce the anti-biofilm effect. All of these results have been published.

[figure not shown]
### 1.3.2 Bald's salve has a promising safety profile in tests with human cells and animal models

We have conducted laboratory research which demonstrates that Bald's salve has a low risk of being toxic to human cells, triggering an excessive inflammatory response, or interfering with wound healing. This work is currently undergoing revision for publication but a preprint is available. The results are summarised below.

First, lab cultures of human skin and immune cells were exposed to the salve. Cultured cells are very sensitive to damage so they are a good 'early warning system' for severe toxicity or immunogenicity. While we saw some cell death, and some release of inflammatory cytokines, this was comparable with death/inflammation induced by exposing the cells to Optrex® antibiotic eyedrops: these contain chloramphenicol, which is known to damage cells grown in the lab although it is perfectly safe to apply to the eye.

We therefore moved to test the salve in an industry-standard *ex vivo* model, and an *in vivo* model, for assessing irritant capacity of substances. The bovine corneal opacity and permeability test is used in the pharmaceutical and cosmetic industries as a standard model of eye irritation. Substances are dropped onto cows' eyes (obtained post-slaughter from a commercial abattoir) and the eyes are then assessed for irritation, visible as a cloudy patch on the cornea which can clear and resolve over time. The salve demonstrated slight irritation to the cornea that resolved within ten minutes. We then used a novel *in vivo* method where test substances are applied to live slugs, and the amount of mucus secreted by the slugs in response to the substance is quantified as a proxy for extent of irritation. A low level of mucus was secreted by slugs exposed to eyesalve, indicating mild mucosal irritation.

Finally, we conducted an *in vivo* wound healing experiment using live mice. A total of 19 mice were administered a full-thickness surgical excision wound and treated by applying 100 µl of the salve (three different batches tested) or 100 µl sterile water to the wound. Each day, the dressing was removed, a further 100 µl of eyesalve or water was added, the wounds were photographed and measured with a wound imaging and documentation system, and the dressing replaced. This continued for 15 days, by which time the wounds had all healed. The area of the wounds reduced daily as shown below, and analysis with linear models showed that there was no difference in healing rates between eyesalve-treated and water-treated groups. All wounds were healed by day 15. There were no visible signs of irritation or inflammation – i.e. there was no reddening of tissue, and the mice did not display signs of irritation. Example images are in press.

**Figure 1.** Wound healing over time in mice treated with water (control, black) or Bald's salve (three batches shown in orange, purple and blue – each batch made with fresh ingredients). Each line shows the change in the area of the wound for an individual mouse.

Given the laboratory and animal study evidence for the potential efficacy and safety of the ancientbiotic, the next stage is to test the liquid in a sample of healthy volunteers. We want to assess safety by undertaking a skin patch test, using Bald's salve, in healthy adults to identify adverse events.

## 1.4 Hypothesis

We hypothesise that a 48-hour exposure to the ancientbiotic will not result in irritation or inflammation in healthy, non-diabetic adults.

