## 1.5 Need for a pilot safety trial

A pilot clinical trial will be conducted with approximately 100 healthy adult volunteers, to assess the safety and tolerability of the ancientbiotic product on human skin. We want to find out whether, after completion of laboratory tests to human cells, there is any suspicion that the ancientbiotic causes inflammation to human cells. We consider this highly unlikely given (1) the data from cytotoxicity, irritation and wound healing assays cited above; and (2) that the product consists entirely of edible household ingredients.

**Study Design:** non-randomised, uncontrolled, Phase I pilot trial.

**Participants:** Adults aged 18-79 years, community-dwelling, male or female, without a diagnosis of diabetes, immune-related disease (asthma, eczema, psoriasis), pregnancy, or recent infection will be recruited. People with known dietary allergies will be excluded. People with Covid-19 infection, Covid-19 symptoms, or who are self-isolating due to Covid-19 exposure, will be excluded.

**Intervention:** Sticking plaster infused with one drop of the liquid Bald's salve ancientbiotic compound, applied to the skin of the upper arm, worn for 48 hours.

**Outcomes:** Adverse skin effects over 48 hours e.g. redness, heat, swelling or other. Type, number (%) and spread/distribution will be recorded. Digital photographs will be taken of any suspected skin reaction.

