## **1.8 Assessment and management of risk**

There will be some risk of experiencing skin redness or irritation from the skin patch test, arising either from application of the Bald's salve or from the sticking plaster. The products within the salve include garlic (active ingredient allicin), onion, wine and bovine bile. We do not anticipate any serious adverse events such as those resulting in death, hospitalisation, life threatening illness or permanent disability. Any participant experiencing any discomfort will be advised to remove the plaster and gently wash the area with soap and water. If symptoms persists, we advise them to visit their GP.

In light of Covid-19, there are also risks associated with contact between participants and the research team. We have taken steps to ensure rules regarding distancing and protection are adhered to. A Perspex sheet will be placed between the attending volunteer and researcher; facial masks will be worn by all personnel and participants. The Perspex sheet will be adapted to allow the participant's upper arm to be accessed for patch test application. Face to face assessment at 48 hours, as originally planned, has been replaced with telephone or video link contact. The study will be administered in keeping with WCTU SOPs for risk assessment and monitoring.

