### **2.2 Trial summary**

Trial overview: Healthy volunteers will be sought by the research team using multiple strategies, including email circular invitations, social media and advertising the study to University of Warwick staff and students during academic term time. We will also seek a broad range of volunteers and will also recruit from the local community via groups (e.g. Women's Institute, activity groups) who have learned of the study via the media or our outreach activities (e.g. FH invited talks planned for January 2021). We will only recruit volunteers who are based in the surrounding locality (Coventry, Leamington, Warwick and Kenilworth). We aim to recruit between 90 to 100 volunteers in total.

After consent and recruitment, a small drop of the Bald's salve (intervention) will be applied onto a sticking plaster and applied to the participant's upper arm.

A fresh batch of the salve will be prepared using garlic and onions sourced from a commercial greengrocer, Pennard Organic white wine sourced from Avalon Vineyard, Somerset, and bovine bile (Merck Millipore catalogue no. B3883 suspended in sterile water). The salve will be passed through a 0.2µm syringe filter prior to use in this study to ensure sterility.

Outcomes will be captured at 48 hours. Due to Covid-19, face to face assessment of all participants will not be undertaken; this will be replaced with telephone or video contact supplemented with email.

Thus, after 48 hours, the participant will be contacted by the research team and asked to report any sign of skin reaction. We will ask participants to send a photographic image of the affected area. Some participants may be contacted by video (MS Teams, Zoom, Google or other video platform at the participant's discretion) for visual assessment of the affected area. We will collect and store photographs only from those reporting signs of redness or irritation and from a small sample of people with no symptoms (n=5), for comparison purposes.

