#### **2.3.1 Objectives**

The objective is to determine the frequency and character of adverse events associated with a patch test of Bald's salve applied to the skin of 90 to 100 human volunteers.

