## 3.2 ADVERSE EVENT MANAGEMENT

### 3.3 Definitions

#### 3.3.1 Adverse Events (AE)

An Adverse Event (AE) is defined as any untoward medical occurrence involving a participant, which does not necessarily have a causal relationship with the intervention or trial.

**Expected AEs**, related to the ancientbiotic intervention, may include:

- Skin redness
- Skin itchiness
- Skin discomfort

We will capture symptoms arising within and at 48 hours.

**Unexpected AEs** related to the ancientbiotic will be recorded via self-report by the participant up to 48 hours or at 48 hours when contacted by the research team.

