## **5 STATISTICAL ANALYSIS**

### **5.1 Power and sample size**

No sample size was calculated for this phase 1 study. The aim is to assess safety of the salve. The primary outcome will be adverse skin effects over 48 hours e.g. redness, heat, swelling or other. Type, number (%) and spread/distribution will be recorded.

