### **5.2.5 Primary outcome analysis**

Data will be summarised and reported in accordance with CONSORT guidelines for RCTs [50]. Type, number (%) and spread/distribution of any adverse events will be reported by age and sex characteristics. Analysis will be undertaken by a senior statistician (NP).

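### The hypothesis of no irritation conflicts with the protocol's own expected events and objective, and 90 to 100 volunteers cannot establish it; it should be restated as estimation of a reaction rate

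*Protocol*

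**What the plan says.** Protocol section 1.4 reads: "We hypothesise that a 48-hour exposure to the ancientbiotic will not result in irritation or inflammation in healthy, non-diabetic adults". No rate, severity or margin qualifies it.

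Other sections of the protocol point a different way:

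- Section 3.3.1 gives a list of expected adverse events "related to the ancientbiotic intervention, may include" skin redness, itchiness and discomfort.
- Section 1.8 says: "There will be some risk of experiencing skin redness or irritation from the skin patch test". It names both the salve and the plaster as possible sources.
- Section 2.8, under new information, has the study carry on if the first 10 volunteers show minor skin reactions or none.
- Section 2.3.1 sets an estimation aim: "The objective is to determine the frequency and character of adverse events associated with a patch test". The Study Summary and section 2.4.1 also speak of the frequency of adverse events.

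On size, section 2.2 says "We aim to recruit between 90 to 100 volunteers in total", and section 1.5 speaks of about 100. Section 5.1 says "No sample size was calculated for this phase 1 study" and gives no statement of precision in its place. Section 2.9.1 confirms that there is no comparator arm.

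On reporting, section 5.2.5 says "Type, number (%) and spread/distribution of any adverse events will be reported by age and sex characteristics". Section 5.2.3 names the same summaries, and section 5.2.4 adds unspecified standard summaries for the primary outcome. None of these sections names a confidence interval, and none rules one out.

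**The concern.** A hypothesis that something will not happen at all can be supported by a finite sample only up to an upper bound. Section 1.4 gives no bound, so a clean result invites the conclusion that the hypothesis is confirmed and that the salve does not irritate. The data would in fact remain compatible with a reaction rate of several percent. The trial's title names infected diabetic ulcers as the intended use, so how a clean result is worded matters to later readers.

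The hypothesis also disagrees with the rest of the protocol. The safety section treats reactions to the salve as expected, the risk section says that some risk exists, and the staggered start is written to proceed through minor reactions. A reader cannot tell whether a few mild reactions would count as the anticipated result or as evidence against the hypothesis.

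**Working it through.** The protocol has no sample size calculation, so there is no figure to reproduce. The check asks what 90 to 100 volunteers can show about a zero rate.

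**Inputs.** n = 90 and n = 100 (section 2.2). No tolerated rate, significance level or expected reaction rate is given, so the true rates below are assumptions. Loss to follow-up is expected (section 5.2.6), but no rate is given.

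**Upper limit when no reaction is seen.** The exact binomial (Clopper-Pearson) upper limit for 0 of n is 1 − 0.025^(1/n) for a two-sided 95% interval, and 1 − 0.05^(1/n) for a one-sided 95% bound.

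| n | Two-sided 95% | One-sided 95% |
|---|---|---|
| 100 | 1 − 0.025^(1/100) = 3.62% | 1 − 0.05^(1/100) = 2.95% |
| 90 | 1 − 0.025^(1/90) = 4.02% | 1 − 0.05^(1/90) = 3.27% |

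The choice of method matters little: the Wilson two-sided limit is 3.7% at n = 100 and 4.1% at n = 90. If only 80 volunteers were evaluable (an assumption), the exact two-sided limit would be 4.5%.

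**Chance of missing a real reaction.** P(no events) = (1 − p)^n.

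| Assumed true rate p | n = 100 | n = 90 |
|---|---|---|
| 1% | 0.99^100 = 36.6% | 0.99^90 = 40.5% |
| 2% | 13.3% | 16.2% |
| 3% | 4.8% | 6.4% |

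**Chance of at least one reaction.** This is 1 − (1 − p)^n. At n = 100 it is 63% for p = 1% and 87% for p = 2%. Even a low true rate is therefore more likely than not to produce an event.

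**What one reaction would show.** The exact two-sided 95% interval for 1 of 100 is 0.03% to 5.4%, and for 1 of 90 it is 0.03% to 6.0%. These are rates from any cause. Section 1.8 allows the plaster as a cause and there is no control patch, so one redness cannot be attributed to the salve with confidence. It would neither support nor overturn a claim about the salve.

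**Sections side by side.** Section 1.4 says that no irritation will result. Section 3.3.1 classes three skin reactions as expected and related, section 1.8 states some risk, and section 2.8 continues after minor reactions. Section 2.3.1 asks how often events occur. The last question has a sensible answer at this sample size (a percentage with an interval). The claim of zero does not.

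**The case against.** The strongest reply is that nothing in the trial depends on section 1.4. There is no test, margin or success criterion, and the objective and primary outcome are already descriptive. On this view the hypothesis is a background expectation, supported by the mouse wound study in section 1.3.2, which saw no visible irritation. The list of expected events serves to classify events for safety reporting and does not predict that they will occur. Interval methods are ordinary content for a statistical analysis plan, which is not shown here.

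Much of this stands, and it rules out three stronger readings that a reader might infer:

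- That a single redness, even one caused by the plaster, refutes the hypothesis. The hypothesis concerns the salve, so a plaster reaction leaves it untouched.
- That the trial cannot answer its own question. Its stated objective is frequency and character of events, which 90 to 100 volunteers can estimate.
- That a result of 0% will be published with no interval. The protocol names only number and percentage, but section 5.2.4 leaves room for more and a separate plan may specify it.

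The reply does not remove the inconsistency within the protocol. A hypothesis with no tolerated rate still stands beside an expected-events list and an estimation objective, and a separate analysis plan would not amend section 1.4.

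**Conclusion.** The point holds as a matter of wording and interpretation. Section 1.4 states an absolute claim that is inconsistent with sections 1.8, 2.8 and 3.3.1 and with the objective in 2.3.1, and the planned sample cannot establish it. With no events, rates up to 3.6% (n = 100) or 4.0% (n = 90) remain compatible with the data on the exact two-sided 95% limit. A true rate of 1% would go unseen with probability 37% or 40%.

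These figures assume that all 90 to 100 volunteers are evaluable and independent; fewer evaluable volunteers would widen the limits. The 1% rate is illustrative, since the protocol gives none. The consequence is limited because no formal test is planned. The absence of an interval is not shown to be an error, so reporting one is a recommendation.

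**What to change.** - **Section 1.4:** replace the hypothesis with an aim that matches section 2.3.1: to estimate the proportion of volunteers with an application-site reaction on the protocol's existing 48-hour outcome, with an exact (Clopper-Pearson) 95% confidence interval. Reconcile this text with sections 1.8, 2.8 and 3.3.1.
- **Section 5.1:** state the precision in place of a sample size calculation: with 90 to 100 evaluable volunteers and no events, the two-sided 95% upper limit is 4.0% to 3.6%.
- **Section 5.2.5:** report the overall percentage with its exact 95% interval, and word the conclusion from a clean result as an upper limit on the reaction rate, not as absence of irritation.

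No further analysis by severity is proposed, because the protocol contains no severity scale on which to base one.

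The cost is wording only, with no added data or volunteers. The one drawback is that a clean result reads slightly less favourably than a bare 0%.
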